## **10 DATA AND SAFETY MONITORING**

Phase 1 studies will be reviewed at the scheduled RPCI Phase 1 meetings and the minutes are forwarded to the IRB for review.

The RPCI Data and Safety Monitoring Board will assess the progress of the study, the safety data, and critical efficacy endpoints. The DSMB will review the study annually and will make recommendations that include but not limited to; (a) continuation of the study, (b) modifications to the design (c) or termination of the study.

## **11 STATISTICAL METHODOLOGY**

This is a Phase 1b/2 study to assess the safety and efficacy of tivozanib therapy in HCC patients. The Phase 1b portion follows a modified 3+3 design (refer to **Section 3.3**), and provides limited toxicity information about tivozanib therapy in this patient population. The Phase 2 portion is a two-stage, single arm, unblinded trial allowing for early termination in case of futility. Phase 1b patients treated at the recommended Phase 2 dose will be included in the Phase 2 trial.

### **11.1 Phase 1b**

To compensate for the current lack of toxicity information about tivozanib treatment in this patient population, the safety cohort begins by enrolling 3 patients at Dose Level 1. Then

modified 3 + 3 decision rules are followed to determine the recommended Phase 2 dose. Dose decision rules are specified in **Section 3.3**. A schematic of the Phase 1b design is shown in **Figure 1**. The recommended Phase 2 dose will be considered tolerable if DLT(s) are observed in at most 1 of 6 patients completing at least 1 treatment cycles at that dose level.

The Phase 1b design requires between 6 and 18 patients. Available information about tivozanib treatment suggests Dose Level 2 will be the recommended Phase 2 dose. Under this scenario, the safety cohort will consist of 9 patients. The 6 safety cohort patients treated at the recommended Phase 2 dose will be included in Stage 1 of the Phase 2 study.

Phase 1b patients who do not complete at least 80% of the prescribed dose in Cycle 1 for reasons other than DLT will be replaced.

## 11.2 Phase 2

The Phase 2 study proceeds in 2 stages, and allows for early stopping for futility. The primary endpoint is the percentage of PFS responders, defined as patients who survive without disease progression (per RECIST criteria) for least 24 weeks past enrollment.

**Stage 1:** Enroll  $n_1 = 19$  patients, including the safety cohort patients treated at the Phase 2 dose. If 9 or fewer PFS responses are observed, the therapy will be deemed ineffective and the study will end. Otherwise, the study will proceed to the second stage.

**Stage 2:** Enroll an additional  $n_2 = 18$  patients. If  $T = 23$  or fewer PFS responses are observed among the total  $n_1 + n_2 = 37$  patients, the therapy will be deemed ineffective; otherwise, it will be concluded that the therapy is promising. Under the null hypothesis of a 50% PFS rate at 24 weeks, the probability of stopping early for futility is 50%. Under the alternative of a 70% PFS rate, this probability is 3.3%. Patients who die or withdraw from the study prior to the 24th week will be counted as events. These patients will not be replaced. The nominal significance level of this design is  $\alpha = 0.05$ .

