### 3.4 Target Accrual and Study Duration

Between 6 and 18 patients will be enrolled in the Phase 1b portion of this study. Six Phase 1b patients treated at the recommended Phase 2 dose will be included in the Phase 2 portion of this study. An additional 31 patients will be enrolled for the Phase 2 portion, for a total Phase 2 sample size of 37. This study is expected to accrue 9 patients to the Phase 1b, for a combined

sample of size of 40 (9+37-6). If 18 patients are enrolled in the Phase 1b, the maximum combined sample size will be 49 (18+37-6).

Accrual is expected to take up to 4 years. The duration the patient will be on study will be approximately 2 years.

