## 11.3 Sample Size Determination

Between 6 and 18 patients will be enrolled in Phase 1b portion. Six Phase 1b patients treated at the recommended Phase 2 dose will be included in the Phase 2 portion of this study. An additional 31 patients will be enrolled for the Phase 2 portion of this study, for a total Phase 2 sample size of 37. This study is expected to accrue 9 patients to the Phase 1b, for a combined sample of size 40 ( $=9+37-6$ ). If 18 patients are enrolled in the Phase 1b, the maximum combined sample size is 49 ( $=18+37-6$ ).

The sample size calculation is based on testing hypotheses concerning the proportion of the treated population alive and disease free 24 weeks after enrollment. Let  $p$  represent the proportion of patients surviving with no evidence of disease progression by RECIST at 24 weeks after enrollment. A true progression rate of less than  $p_0 = 0.50$  is considered unacceptable and evidence of such will deem the treatment not worthy of further study. The null and alternative hypotheses to be tested are  $H_0: p = p_0$  versus  $H_1: p > p_0$ .

This 2-stage design requires a potential total of 37 patients to achieve approximately  $1 - \beta$  power to detect a difference of at least  $\Delta$  percentage points ( $p_0$  versus  $p_0 + \Delta$ ). For calculations in this study,  $p_0 = 0.50$ ,  $\alpha = 0.05$ ,  $1 - \beta = 0.80$  and  $\Delta = 0.20$ . With these design parameters, the sample size was calculated using the web calculator located at <http://cryptnet.net/kepner/>.

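### Does replacing under-dosed Phase 1b patients upset the Phase 2 count of six plus 31, or let an early failure leave the efficacy sample?

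*Combined protocol and SAP*

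**What the plan says.** Sections 6.5 and 11.1 carry the same replacement rule: Phase 1b patients "who do not complete at least 80% of the prescribed dose in Cycle 1 for reasons other than DLT will be replaced". In 11.1 it accompanies the tolerability criterion, which is met if "DLT(s) are observed in at most 1 of 6 patients completing at least 1 treatment cycles at that dose level".

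The head count appears in several places:

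- Section 11.1: "The 6 safety cohort patients treated at the recommended Phase 2 dose will be included in Stage 1 of the Phase 2 study".
- Section 11.3, and the synopsis in the same words: "Six Phase 1b patients treated at the recommended Phase 2 dose will be included in the Phase 2 portion of this study".
- Section 3.4: "An additional 31 patients will be enrolled for the Phase 2 portion, for a total Phase 2 sample size of 37".
- Section 3.3.1 sets only a minimum of six at the recommended dose. It also records that 1 mg daily was the dose taken forward.

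Other passages define who is analyzed, without giving a number of Phase 1b patients:

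- The opening of section 11: "Phase 1b patients treated at the recommended Phase 2 dose will be included in the Phase 2 trial".
- Section 11.2 sets n1 = 19, "including the safety cohort patients treated at the Phase 2 dose", and a total of 37, with futility at 9 or fewer of 19 and failure at 23 or fewer of 37.
- Section 11.2 also says: "Patients who die or withdraw from the study prior to the 24th week will be counted as events". The next sentence says such patients are not replaced.
- Section 11.6 defines the efficacy sample as everyone enrolled in Phase 2 plus the Phase 1b patients treated at the recommended dose. It assesses the primary endpoint in all enrolled patients and counts removals for non-compliance as events. The synopsis repeats the all-enrolled rule.

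**The concern.** Replacement makes sense for counting DLTs, because a patient who took too little drug says little about tolerability. The same patients are then reused in the efficacy test, where leaving out someone who stopped early is a familiar source of bias.

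Two things look wrong. First, the arithmetic of six plus 31 holds only if nobody at the Phase 2 dose was replaced. With one replacement there are seven treated patients, and a seventh has no obvious place in six plus 31. Second, 11.1 replaces a patient who, for example, dies of disease in week 2, while 11.2 counts such a patient as an event and does not replace them.

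If the replaced patient were dropped and a later patient took the place, the Stage 1 count and the final count would both tilt toward the drug. The trial is single-arm and unblinded with cut-offs at exact counts, so one patient can decide the result.

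**Working it through.** **The stated design.** Inputs are from 11.2 and 11.3: n1 = 19, n2 = 18, stop if X1 ≤ 9, declare promising if X1 + X2 ≥ 24, p0 = 0.50, p1 = 0.70. With X1 ~ Bin(19, p) and X2 ~ Bin(18, p):

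- P(stop early) = P(X1 ≤ 9) = 0.500 at p = 0.5 and 0.0326 at p = 0.7 (the plan states 50% and 3.3%).
- P(promising) = Σ over x = 10 to 19 of P(X1 = x) · P(X2 ≥ 24 − x) = 0.0487 at p = 0.5 and 0.803 at p = 0.7 (the plan states 0.05 nominal and 0.80).

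The plan's figures reproduce.

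**The head count.** Let k be the number of patients replaced at the Phase 2 dose. The documents do not give k.

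- k = 0: 6 + 31 = 37 and 6 + 13 = 19. Every passage agrees.
- k = 1: treated at the dose = 7. Enrolling 31 more would give 38, a size for which 11.2 has no cut-off. Holding to 11.2 gives 7 + 12 = 19 and 7 + 30 = 37. The cut-offs apply as written, and alpha 0.0487 and power 0.803 do not move.

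**Who is replaced.** The trigger is dose taken. A full cycle is 21 capsules (section 6.1), and 0.8 × 21 = 16.8, so fewer than 17 doses triggers it. A patient who misses five doses for a non-DLT reason takes 16 and is replaced, yet may continue and be progression-free at week 24. Replacement is therefore not the same as early failure.

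**Size if a replaced patient were nevertheless dropped.** The documents give no replacement rate, so q per patient is an assumption. Let r be the share of replaced patients who are certain failures, with the rest responding at 50%. Under a true all-treated rate of 50%, the six retained patients respond at

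p_kept = (0.5 − 0.5·q·(1 − r)) / (1 − q).

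Stage 1 is then Bin(6, p_kept) + Bin(13, 0.5), and Stage 2 is Bin(18, 0.5).

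| Assumed q | P(any of six replaced) = 1 − (1 − q)^6 | Alpha, r = 1 | Early stop under H0, r = 1 | Alpha, r = 0.5 | Alpha, r = 0 |
|---|---|---|---|---|---|
| 1% | 0.059 | 0.0497 | 0.494 | 0.0492 | 0.0487 |
| 3% | 0.167 | 0.0519 | 0.483 | 0.0503 | 0.0487 |
| 6.8% | 0.344 | 0.0564 | 0.460 | 0.0524 | 0.0487 |

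The 6.8% is 1 − 0.5^(17/168): exponential PFS with 50% at 24 weeks (168 days) and failure before day 17. It is an illustration, not a bound. Withdrawals also count as events, which could raise it. The first on-study CT is at Cycle 3 (Table 4), so few progressions would be documented that early, which could lower it. At q = 10% with r = 1, alpha would be 0.061. With r = 1, alpha passes 0.05 only once q exceeds 1.29%.

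**The case for a change.** The strongest case for a change is that the contradiction is real and 11.6 alone does not settle it. For any k of at least 1, six, 31, 37 and the all-treated sample cannot all hold. No sentence limits replacement to DLT evaluability. Keeping a certain failure as a 38th patient while leaving the cut-offs at 9 and 23 gives the same decision as dropping that patient, so the 31 would have to fall as well. A wording edit would cost nothing.

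The inconsistency stands, and so does the clash between 11.1 and 11.2 over whether an early death is replaced. The claim that the text allows a failure to be discarded does not stand. Leaving a patient out would breach the all-enrolled rule in the synopsis and 11.6, and the event rule in 11.2. A 38th patient would breach the total of 37 that goes with the cut-off of 23. Six and 31 sit among planning figures, such as 6 to 18 in Phase 1b and an expected 9. The sentence in 11.1 about the six follows a scenario in which Dose Level 2 is chosen, whereas 3.3.1 records that 1 mg was taken forward. The replacement rule is written for Phase 1b patients and, in 11.1, stands in the section that defines tolerability.

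**Conclusion.** No change follows. The counts of six and 31 are planning numbers that assume no replacement at the Phase 2 dose. The operative rules are in 11.2 and 11.6, and an analyst who applies them keeps any replaced patient inside 19 and 37 and enrolls 37 minus the number already treated at the dose. That preserves alpha 0.0487 and power 0.803.

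Bias needs three things together: a replacement at 1 mg, which the documents do not report; a reason linked to outcome; and an analysis that departs from 11.6. If all three occurred, alpha would be between 0.0497 and 0.0564 for assumed replacement rates of 1% to 6.8% with every replaced patient a failure, and less if some were not. If nobody was replaced, 6 + 31 = 37 and the point disappears. The conclusion rests on reading 11.2 and 11.6 as governing the test, which is the only reading that respects the fixed sizes and cut-offs and the all-enrolled rule.

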## 11.3 Sample Size Determination

Between 6 and 18 patients will be enrolled in Phase 1b portion. Six Phase 1b patients treated at the recommended Phase 2 dose will be included in the Phase 2 portion of this study. An additional 31 patients will be enrolled for the Phase 2 portion of this study, for a total Phase 2 sample size of 37. This study is expected to accrue 9 patients to the Phase 1b, for a combined sample of size 40 ( $=9+37-6$ ). If 18 patients are enrolled in the Phase 1b, the maximum combined sample size is 49 ( $=18+37-6$ ).

The sample size calculation is based on testing hypotheses concerning the proportion of the treated population alive and disease free 24 weeks after enrollment. Let  $p$  represent the proportion of patients surviving with no evidence of disease progression by RECIST at 24 weeks after enrollment. A true progression rate of less than  $p_0 = 0.50$  is considered unacceptable and evidence of such will deem the treatment not worthy of further study. The null and alternative hypotheses to be tested are  $H_0: p = p_0$  versus  $H_1: p > p_0$ .

This 2-stage design requires a potential total of 37 patients to achieve approximately  $1 - \beta$  power to detect a difference of at least  $\Delta$  percentage points ( $p_0$  versus  $p_0 + \Delta$ ). For calculations in this study,  $p_0 = 0.50$ ,  $\alpha = 0.05$ ,  $1 - \beta = 0.80$  and  $\Delta = 0.20$ . With these design parameters, the sample size was calculated using the web calculator located at <http://cryptnet.net/kepner/>.

#### **11.4 Randomization**

This is a nonrandomized study.

#### **11.5 Demographics and Baseline Characteristics**

Descriptive statistics and statistical plots will be used to summarize changes in biomarkers levels in blood and changes in viral titers. The paired t-test, Wilcoxon signed-rank test, and McNemar's test will be used for within-patient comparisons of changes in biomarker levels across times. The repeated measures modelling may be used to explore the effects of exogenous factors (i.e., diabetes, hepatitis, cirrhosis, etc.) on the changes in biomarkers and viral titers. The effects of biomarkers on clinical benefit rate (CR+PR) will be assessed using logistic regression and the effects on time-to-event data (overall survival and progression free survival) will be estimated by Cox model.

#### **11.6 Efficacy Analysis**

The efficacy sample includes all patients enrolled in the Phase 2 study, plus Phase 1b patients treated at the recommended Phase 2 dose. Patients removed from the study for non-compliance will be counted as events in the efficacy analyses.

The primary endpoint will be progression free survival at 24 weeks using standard RECIST criteria. All enrolled patients will be included in assessment of the primary endpoint. Time-to-progression will be descriptively analyzed using standard Kaplan-Meier estimation along with the corresponding descriptive statistics and 95% confidence intervals.

Secondary endpoints will include, overall survival, toxicity, clinical benefit rate (CR+ PR+ SD). Correlative endpoints will also include AFP response, antiviral effect (if any in those with HBV or HCV associated HCC) and exploration for any correlation between drug exposure (assessed by steady state PK) and response/ survival and toxicity by quartiles of drug exposure will be exploratory.

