## **6.5 Compliance**

Patients will be instructed to record date for each day and the total number of pills taken each day (**Appendix E**). Dosing compliance will be monitored at each clinic visit. Phase 1b patients who do not complete at least 80% of the prescribed dose in Cycle 1 for reasons other than DLT will be replaced. Otherwise, if a patient has 2 consecutive cycles of less than 50% compliance, the patient will be deemed non-compliant and come off study. At the discretion of the investigator, if the patient is benefiting from the treatment the patient may continue on study. Patients who come off study, due to non-compliance, will not be replaced.

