
1 Performed within 2 weeks prior to treatment start and prior to receiving any study-related procedures.
 
2 Height collected at baseline only.
 
3 Hematology (i.e., complete blood count (CBC) with differential, absolute neutrophil count (ANC), and platelets).
 
4 Chemistry (comprehensive metabolic panel (i.e.; AST, ALT, total bilirubin, alkaline phosphatase, creatinine, potassium, glucose, and calcium) and serum albumin).
 
5 Only test if AFP was elevated at baseline.
 
6 Refer to Section 7.10.
 
7 Pre-dosed cycle 1 day 1, cycle 3 day 1, when the patient progresses/comes off study drug or at 1 year whichever occurs first. Refer to Section 7.11.
 
8 Performed within 1 week prior to treatment start.
 
9 Only if last CT scan was more than 28 days prior to end of treatment.
 
10 Patients will be administered tivozanib in clinic following their pre-dose pharmacokinetic/pharmacodynamic sample.
 
11 Medications ongoing within 1 week prior to first dose of study drug.
 
12 CT every 2 cycles starting with cycle 3, with maximum of 10 weeks apart.
 
13 Collect viral load, pre-treatment, if either (or both) HBsAg or Hep C Ab with verification are positive & every 2 cycles starting with cycle 3.
 
14 Every 2 cycles starting with cycle 3.
 
15 Patients will be followed for overall survival, every 6 months by medical record review
 
16 CT scan within 4 weeks prior to treatment start.
 
17 Only if unknown
							

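### Section 11.6 counts non-compliance removals as events without naming an endpoint or a time limit; read literally, this reaches overall survival and time-to-progression

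*Combined protocol and SAP*

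**What the plan says.** Section 11.6 (Efficacy Analysis) defines the efficacy sample and then gives the rule: "Patients removed from the study for non-compliance will be counted as events in the efficacy analyses". It goes on to name 24-week PFS as the primary endpoint. It adds that "Time-to-progression will be descriptively analyzed using standard Kaplan-Meier estimation along with the corresponding descriptive statistics and 95% confidence intervals", and it lists overall survival and clinical benefit rate among the secondary endpoints.

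Four other places bear on this:

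- **Section 11.2** has its own event rule, which carries a time limit: "Patients who die or withdraw from the study prior to the 24th week will be counted as events".
- **Section 6.5** defines the removal: "if a patient has 2 consecutive cycles of less than 50% compliance, the patient will be deemed non-compliant and come off study". The investigator may keep such a patient on study if the patient is benefiting.
- **Table 4, footnote 15** continues survival follow-up after treatment: "Patients will be followed for overall survival, every 6 months by medical record review".
- **Section 11.5** plans biomarker models in which "the effects on time-to-event data (overall survival and progression free survival) will be estimated by Cox model".

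No section defines an event or a censoring rule for overall survival or time-to-progression.

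**The concern.** Imputing failure suits a binary endpoint assessed at a fixed week. It does not suit overall survival, where the event is death. A patient removed for missed doses may be alive, and the six-monthly record review should make the true vital status obtainable. Coding that patient as an event would replace an observable outcome with a false one.

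In time-to-progression, the rule would enter a progression that no scan has documented. In the primary endpoint, the missing time limit conflicts with Sections 3.1 and 11.2. Under those, a patient alive and progression-free for at least 24 weeks is a responder, whatever happens to compliance later.

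The Cox models in Section 11.5, and the exploration of exposure against survival in Section 11.6, would inherit the same event times. Poor compliance can lower exposure and, through this rule, also generate an event. Part of an exposure-survival association could then come from the coding.

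**Working it through.** **1. The plan's own design figures.** Inputs from Section 11.2: n1 = 19, stop at 9 or fewer responders; n2 = 18, ineffective at 23 or fewer of 37. Null rate 0.50 and alternative 0.70 (Sections 11.2 and 11.3).

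- Early stopping: the sum over x = 0 to 9 of C(19,x) p^x (1−p)^(19−x). This gives 0.500 at p = 0.50 and 0.0326 at p = 0.70. The plan states 50% and 3.3%.
- Declared promising: the sum over x = 10 to 19 of P(X1 = x) × P(X2 ≥ 24 − x), with X1 ~ Bin(19,p) and X2 ~ Bin(18,p). This gives 0.0487 at p = 0.50 and 0.803 at p = 0.70. The plan states 0.05 and 80%.

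The figures reproduce. They describe a binary responder count, so confining the rule to that endpoint leaves them as they are.

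**2. What the text permits.**

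| Question | Section 11.2 rule | Section 11.6 rule |
|---|---|---|
| Endpoint | 24-week responder status | none named |
| Time limit | before week 24 | none |
| Trigger | death or withdrawal | non-compliance removal |

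Two 28-day cycles must pass before removal is possible, so the earliest is about week 8. Nothing sets a latest time.

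**3. Illustrative size.** The documents give no non-compliance rate, so 1, 2 or 4 removals among 37 are assumed. Other assumptions:

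- Times are exponential. The overall survival median is 10.7 months, the figure Section 1.1 quotes for sorafenib. The time-to-progression median is 24 weeks, from the PFS expectation in Section 2 (24/4.345 = 5.52 months).
- Removal is uniform over months 2–6 (overall survival) or 2–5.5 (time-to-progression), among patients still event-free at that time. It is unrelated to prognosis.
- Follow-up is otherwise complete.

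Each entry is the middle value of the Kaplan-Meier median over 4,000 simulated trials, in months.

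| Removals | OS: followed to death | OS: coded as death | OS: censored | TTP: followed to progression | TTP: coded as progression | TTP: censored |
|---|---|---|---|---|---|---|
| 1 | 10.72 | 10.15 | 10.97 | 5.55 | 5.23 | 5.63 |
| 2 | 10.73 | 9.56 | 10.52 | 5.53 | 4.95 | 5.59 |
| 4 | 10.73 | 8.46 | 10.83 | 5.54 | 4.48 | 5.53 |

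Fall in median OS: 10.72 − 10.15 = 0.57; 10.73 − 9.56 = 1.17; 10.73 − 8.46 = 2.27 months.

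Fall in median time-to-progression: 5.55 − 5.23 = 0.32; 5.53 − 4.95 = 0.58; 5.54 − 4.48 = 1.06 months.

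Because removal was simulated as unrelated to prognosis, the censored columns say nothing about bias from informative removal.

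**The case against.** The best defence is that the sentence was meant for the 24-week endpoint only. Its wording echoes Section 11.2, where counting as an event plainly means failing 24-week PFS. The synopsis paragraph on efficacy analysis covers only the 24-week response rate. In Section 11.6 the sentence comes just before the primary endpoint, and time-to-progression is then given standard Kaplan-Meier estimation. An experienced statistician would be unlikely to code a living patient as dead on the strength of this sentence. All of that is fair and supports reading it as loose drafting. It does not remove the gap: the text refers to efficacy analyses in the plural, and no other event rule exists for overall survival or time-to-progression.

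The defence is stronger on time-to-progression. Table 4 schedules no scans after the end-of-treatment visit, so later progression is generally unobserved. Section 6.5 lets patients judged to be benefiting stay on, so those removed may have a worse outlook. Censoring them may bias the estimate upward, while event-coding is conservative. That stands, and it is why the fix keeps event-coding as a sensitivity analysis.

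The removal counts are also assumed. Section 6.5 requires two consecutive poor cycles and allows an exception, so there may be no removals at all.

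**Conclusion.** The point holds as a rule stated too broadly. Taken literally, it gives wrong event status for overall survival, undocumented progressions in time-to-progression, and possible failure status for a patient who has already met the 24-week definition. The bias runs against tivozanib. The go/no-go rule rests on the 24-week responder count, and its stated operating characteristics stand. The falls in median of roughly 0.6 to 2.3 months (overall survival) and 0.3 to 1.1 months (time-to-progression) rest wholly on the assumed counts, removal times and exponential form. They are not forecasts.

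A reader might infer three stronger conclusions that the documents do not support:

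- **That the plan definitely records living patients as dead in every efficacy analysis.** Section 11.6 does not say every analysis and does not mention deaths. The narrower intent is plausible.
- **That counting removals as failures is wrong in the primary endpoint.** There it is a legitimate conservative choice, consistent with Section 11.2.
- **That progressions coded this way are known to be false.** Without scheduled scans after treatment ends, they are undocumented, which is a weaker statement.

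**What to change.** Replace the sentence in Section 11.6 with three rules:

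1. **24-week PFS.** Patients removed for non-compliance before week 24 without documented progression count as non-responders in the binary endpoint. Removal after week 24 does not change responder status.
2. **Overall survival.** Only death is an event. Patients not known to have died are censored at the date last known alive, using the existing six-monthly record review, which continues after removal.
3. **Time-to-progression and PFS.** Only documented progression is an event, with death added for PFS. Other patients are censored at the last evaluable scan. Removal-as-event is reported as a sensitivity analysis, because removal may be informative.

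State that the Cox models use the same definitions, and report the number and timing of non-compliance removals. The cost is a few sentences and one extra descriptive analysis. Sample size and decision boundaries do not change, and no new data collection is needed.
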